5.6.4. Clinical Laboratory Evaluations

Clinical laboratory results will be summarized using SI Units. Laboratory measurements will be summarized for each parameter. Descriptive statistics (n, mean, standard deviation, median, minimum, and maximum) will be presented for clinical chemistry, hematology, and coagulation parameters at each scheduled visit. Change from baseline will be summarized in a similar manner.

Laboratory test results will be graded by NCI CTCAE (Version 5.0). Shift tables will be presented for each laboratory parameter to display the shift from baseline grade to the worst post-baseline grade. Summary tables will be provided presenting the number and percentage of patients for each laboratory test by baseline grade and worst post-baseline grade. All post-baseline assessments (including unscheduled visits) will be used to determine the worst post-baseline grade.

For qualitative urinalysis parameters and summary tables will be provided presenting the number and percentage of patients for each parameter and scheduled visit. If any quantitative urinalysis parameters will be collected, descriptive statistics will also be presented at each parameter and scheduled visit.

All clinical laboratory data will be presented in by-patient listings.

The laboratory tests of hematology, serum chemistry, coagulation, and urinalysis are listed in [Table 8](#).

Table 8: Laboratory Tests

Assessment	Test Items
Hematology	Red blood cell (RBC) count, hemoglobin, hematocrit, platelets, white blood cell (WBC) count with differential, neutrophils (ANC), lymphocytes, monocytes, eosinophils, basophils
Serum chemistry	AST, ALT, ALP, total bilirubin, direct bilirubin, albumin, lipase, amylase, LDH, triglyceride, total cholesterol, creatinine, BUN, Na, K, Cl, Serum Calcium, Ca (corrected value), Mg, blood glucose, C reactive protein (CRP), creatinine clearance (if there is a measured value, use the measured value) or eGFR. For a calculated CrCl value, use the Cockcroft-Gault formula: Male: $CrCl = \frac{(140 - [insert\ age\ in\ years]) \times [insert\ weight\ in\ kg]}{72 \times [insert\ serum\ creatinine\ in\ mg/dL]}$ Female: $CrCl = [\frac{(140 - [insert\ age\ in\ years]) \times [insert\ weight\ in\ kg]}{72 \times [insert\ serum\ creatinine\ in\ mg/dL]}] \times 0.85$
Coagulation	PT-INR, APTT, and fibrinogen
Urinalysis	Qualitative: Urine protein, sediment, occult blood by dipstick or laboratory. Quantitative: If urine protein is 2+ to 4+, add urinary β 2-microglobulin and proteinuria.

For a calculated creatinine clearance (CrCl) value, use the Cockcroft-Gault formula:

Male CrCl (mL/min) = $\text{weight (kg)} \times (140 - \text{age (years)}) / [72 \times \text{serum creatinine (mg/dL)}]$

Female CrCl (mL/min) = male CrCl \times 0.85

5.6.5. Vital Signs and Body Weight

Vital sign measurements include systolic blood pressure (mmHg), diastolic blood pressure (mmHg), pulse rate (beats per minute), body temperature (celsius), and body weight (kg). Each vital sign parameter will be summarized with descriptive statistics by scheduled time point. Change from baseline will be summarized in a similar manner.

All vital sign data will be presented in by-patient listings.

5.6.6. Electrocardiograms

ECGs are to be performed using local machines. Additionally, in part A1, ECGs will also be obtained using central ECG machines, according to the schedule of assessments. ECGs are to be performed in triplicate from Cycle 1 Day 1 to Cycle 3 Day 1. Investigators are to review all ECGs, regardless of whether these are from local or central ECG machines, and record findings

in the eCRF and these will be summarized and listed. ECG interpretation (abnormal, clinical significance) is to be performed by the investigator on all ECGs. ECGs performed as part of the time matched exposure/QT analysis will also be read by central cardiologists.

The safety ECG analysis will be done using the All Treated analysis population. Central ECG measurements include HR, RR interval, QT interval and its Fridericia's correction. QTcF (Fridericia's correction) is calculated as $QT/RR^{0.33}$. Screening ECG, performed locally, will have QTcF reported. This parameter will be summarized using descriptive statistics. For central ECGs, each ECG parameter will be summarized with descriptive statistics by scheduled time point. For ECG measurements collected in triplicate at nominal timepoints, the mean of the triplicate measurements will be used in the analysis. Changes from baseline will be summarized in a similar manner. Interpretations based on central cardiologist review will be summarized and listed. Shift tables will present changes from baseline in ECG interpretation based on investigator assessment (categorized as normal, abnormal not clinically significant, abnormal clinically significant) and based on central cardiologist assessment (normal, abnormal significant, abnormal insignificant) to the worst post-baseline result.

Listings will display central and local ECGs with visits/timepoints.

For central ECGs, in addition, the number and percentage of patients with at least one post-baseline abnormal ECG result in QTcF during on-treatment period will be summarized. abnormal ECG results in QTcF will be categorized as follows:

Absolute QTcF interval prolongation:

- Maximum Post-baseline Value ≤ 450 msec
- Maximum Post-baseline Value $> 450 - 480$ msec (with baseline QTc interval ≤ 450 msec)
- Maximum Post-baseline Value $> 480 - 500$ msec (with baseline QTc interval < 470 msec)
- Maximum Post-baseline Value > 500 msec

Change from baseline in QTcF interval:

- Maximum Increase from baseline ≤ 30 msec
- Maximum Increase from baseline $30 - 60$ msec
- Maximum Increase from baseline > 60 msec

All ECG data will be presented in by-patient listings.

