3.2. Phase 1 Dose Expansion – Part B

Objectives	Endpoints
Phase 1 Dose Expansion	
Primary	

 To explore the efficacy of TAS3351 	
 ORR per RECIST v1.1 by independent central review (ICR)
Secondary	

 To confirm the safety and tolerability of TAS3351 at the RP2D and dosing schedule 	
 AEs, including SAEs, clinical laboratory tests, vital signs, and 12-lead ECGs graded according to CTCAE v5.0

 To further explore the anti-tumor efficacy of TAS3351 	
 DoR, PFS, and DCR by ICR ORR, DoR, PFS, and DCR by Investigator assessment Intracranial ORR (icORR) and DoR (icDOR) by ICR and Investigator assessment Overall survival (OS)
Exploratory	

 To explore biomarkers for TAS3351 including their potential association with efficacy 	
 Biomarkers from tumor tissue and blood samples, including (but not limited to) DNA/RNA, protein, and cfDNA analysis

 To explore the potential exposure-response associations for efficacy and safety 	
 Exposures estimated by Population PK model and selected efficacy and safety measures

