7. STUDY ASSESSMENTS

7.1. Study Assessments and Procedures

The Schedule of Events (Section 1.3) summarizes the frequency and timing of all study assessments applicable to this study.

Descriptions of the study assessments required are presented in Table 12.

Table 12: Study Assessments

Assessment	Details
General Study Assessments	
Written informed consent/consent for study continuation	Date when written informed consent was obtained.
Review of inclusion/exclusion criteria	Eligibility must be assessed during the screening period and should be confirmed prior to the first dose of study drug as clinically indicated. See Sections 5.1 and 5.2.
Demographics/medical history	Sex, age, race/ethnicity, clinical diagnosis, date of diagnosis, method of diagnosis, prior cancer therapy, and relevant medical history (past and concurrent).
Baseline signs and symptoms	Signs and symptoms which occurred after signing of ICF but before administration of first dose of TAS3351.
Concomitant medication/concomitant therapy	Medication/therapy with period and the reason of concomitant use (including blood and blood products). Include all medications/therapies administered from the time ICF is signed through 30 days after administration of the last dose of TAS3351 or until the start of new anticancer therapy.
Compliance	Drug accountability of investigational drug. See Section 6.3 and Section 6.7.3.
Safety	
Physical examination	Physical examinations at screening include assessments of general appearance, skin, head and neck (including ears, eyes, nose and throat), respiratory, cardiovascular, abdomen, lymph nodes, thyroid, musculoskeletal (including spine and extremities), and neurological systems. Targeted symptom directed physical examinations may be utilized on the basis of clinical observations at subsequent visits. Examination of skin should be performed at each timepoint indicated in the Schedule of Events.
AE monitoring	See Section 10.
Local and central ECGs	Resting, semi-recumbent 12-lead ECGs; triplicates at baseline, Cycles 1-3, and as clinically indicated (eg, for QT prolongation, see dose modifications in Section 6.2.1.2); RR interval (heart rate), QT interval, QTcF interval and abnormal finding by 12-lead ECG. See Section 7.1.2.

Assessment	Details
Vital signs, height and body weight	Systolic and diastolic blood pressure, pulse rate, body temperature, height (for body mass index calculations, recorded at baseline only) and body weight.

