Electrocardiograms (ECGs) will be collected using a 12-lead tracing. Patients should be in supine position in a rested and calm state for at least 10 minutes before ECG assessment is conducted. If the patient is unable to be in the supine position, the patient should be in most recumbent position as possible. ECGs should be performed on D1 of every cycle and more frequently for patients in Part A1 during the PK lead in period (for PK lead in, see Table 13). For ECGs during Extension, see Table 3.

All ECGs should be performed in triplicate on Day 1 of Cycles 1 to 3 for all patients in Parts A1, A2, B and C. Patients in Part A1 will have additional triplicate ECGs performed during selected time points of the PK Lead-in period. After C3D1, ECGs are not required to be performed in triplicate unless clinically indicated. ECGs should be run consecutively, prior to blood draws or other invasive procedures. An ECG machine with the capacity to calculate standard intervals automatically should be used. If an abnormal ECG finding at screening or baseline is considered to be clinically significant by the Investigator, it should be reported as a concurrent medical history condition. If there is a clinically significant abnormal ECG finding during the treatment period, this should be recorded on the AE eCRF, according to standard AE collection and reporting processes.

For Parts A2, B, and C, all ECGs will be performed using local ECG machines. Patients in Part A1 will have both local and central ECGs (see [Table 13](#)).

For central ECGs in Part A1 (see Schedule of Events; [Table 1](#)), the Investigator or delegate will review all ECGs for any on treatment decisions. Once signed, the original ECG tracing will be retained with the patient's source documents. All digital ECG data will be transferred electronically for central analysis of heart rate, PR, R-R, and QT intervals by an external cardiologist.

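### SAP 5.6.6 builds its on-treatment QTcF tables from central ECGs only, so no Part A2 or Part B patient and no ECG from Cycle 2 onward can enter them

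*SAP*

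**What the plan says.** **SAP 5.6.6.** The safety ECG analysis is assigned to the All Treated population. The numeric output is then tied to source:

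- By-visit statistics: "For central ECGs, each ECG parameter will be summarized with descriptive statistics by scheduled time point". The change-from-baseline sentence follows on from this one.
- Outlier table: "For central ECGs, in addition, the number and percentage of patients with at least one post-baseline abnormal ECG result in QTcF". Its categories are absolute QTcF (cut points 450, 480 and 500 msec) and increase from baseline (cut points 30 and 60 msec).
- Local ECGs: "Screening ECG, performed locally, will have QTcF reported". This is the only local QTcF value named for descriptive summary. Local on-treatment ECGs appear in listings and in the shift table of the investigator's normal/abnormal reading.

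**Protocol, who has central ECGs.** Table 1 gives central ECGs to Part A1 only. Section 7.1.2 states: "For Parts A2, B, and C, all ECGs will be performed using local ECG machines".

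**Protocol, what is measured and promised.** Table 12 covers local and central ECGs together and requires "RR interval (heart rate), QT interval, QTcF interval and abnormal finding by 12-lead ECG". The Part B secondary safety endpoints in Section 3.2 include "12-lead ECGs graded according to CTCAE v5.0". Section 12.7.4.2, which applies to all parts, says that ECG results at the scheduled time points will be analysed.

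**The concern.** QT prolongation is a named risk in the protocol (hERG IC50 of 860 nmol/L and a QTc effect in the dog telemetry study). Part B exists partly to confirm safety at the RP2D. The usual table for judging such a risk counts patients beyond fixed QTcF limits. Here that table draws only on escalation patients, spread over several dose levels, in their first weeks of treatment. The backfill and expansion patients, and everyone's longer exposure, are missing from it.

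There is also a denominator problem. SAP 5.1 produces summaries for A1, A2, A and B, and 5.6.6 uses All Treated. The A2 and B versions of the outlier table would then have no data. In the Part A version, A2 patients could be counted below the line without being able to appear above it.

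**Working it through.** The plan states no figure on this point, so there is none to reproduce. The check traces which ECGs can reach the tables.

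**1. Scheduled central ECGs (protocol Tables 13 and 14; the footnote makes a time point central unless marked otherwise).**

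| Part A1 schedule | Central ECG times | Total | After baseline |
|---|---|---|---|
| QD | Day -3: pre-dose, 1, 2, 4, 8, 24, 72 h; C1D15: pre-dose, 1, 2, 4, 8, 24 h | 7 + 6 = 13 | 12 |
| BID | C1D1: pre-dose, 1, 2, 4, 8 h; C1D15: pre-dose, 1, 2, 4, 8 h | 5 + 5 = 10 | 9 |

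The last central ECG under QD is 24 h after the C1D15 dose, nominally 3 + 14 + 1 = 18 days after the first dose. Under BID it is 8 h on C1D15, 14 days after the first dose. The ±3-day window on the Day 15 visit can shift these dates, but not into Cycle 2.

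**2. Scheduled local ECGs.** In A1, C2D1 and C3D1 are marked local. In A2 and B, every Table 13 time point is local: pre-dose and 2 h on C1D1 and C2D1, and pre-dose on C3D1. Table 1 requires an ECG on Day 1 of every cycle in all parts.

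**3. Patients who can enter the tables (planned numbers, SAP 3.2 and 3.3).**

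- Two Part B cohorts: 40 + 20 + 40 = 100 patients. Excluded: 20 + 40 = 60, or 60/100 = 60%.
- One Part B cohort: 40 + 20 + 20 = 80 patients. Excluded: 20 + 20 = 40, or 40/80 = 50%.
- ECGs from Cycle 2 onward that can enter: none, in any part.

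**4. Denominator.** Suppose two A1 patients exceed 500 msec. Among patients with central data the rate is 2/40 = 5.0%. Over an All Treated Part A denominator it is 2/(40 + 20) = 3.3%.

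**5. Illustration at the RP2D.** The chance that the table shows at least one outlier is 1 − (1 − p)^n. All inputs here are assumptions: true incidence p from 1% to 5%; 6 to 15 A1 patients at that dose (15 is the protocol's maximum per level); 10 A2 and 20 Part B patients added.

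| p | A1 only, n = 6 | A1 only, n = 15 | With A2 and B, n = 36 | With A2 and B, n = 45 |
|---|---|---|---|---|
| 1% | 6% | 14% | 30% | 36% |
| 3% | 17% | 37% | 67% | 75% |
| 5% | 26% | 54% | 84% | 90% |

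For example, 1 − 0.97^6 = 0.167 and 1 − 0.97^36 = 0.666. The calculation gives every patient the same chance of detection. That flatters the added patients early on, because A2 and B have fewer post-dose ECGs in Cycle 1 than A1. It also describes one table, not whether a case is reported anywhere.

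**The case against.** A reader might infer that QT effects in A2 and B go unmonitored, or that a marked prolongation there would go unreported. The documents do not support that. Protocol 7.1.2 requires a clinically significant abnormal ECG on treatment to be recorded as an adverse event. Adverse events are CTCAE-graded, and SAP 5.6.2 tabulates them by dose cohort, for any grade and Grade 3 or higher, and by whether they led to interruption, reduction or discontinuation. The investigator-interpretation shift table uses the worst post-baseline reading, and all ECG data are listed.

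Nor is there a flat breach of protocol 12.7.4.2. It promises analysis of ECG results without prescribing an outlier table, and the shift table is an analysis of a kind.

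Preferring central readings for numeric work is also defensible, because local machine readings are noisier. The main quantitative QT analysis, the concentration-QTcF model in SAP 5.6.7, uses triplicate means matched to plasma samples and predicts the mean change at each dose level.

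Finally, because the SAP mentions reported QTcF only for the local screening ECG, a reader might conclude that on-treatment local QTcF is absent from the database. The eCRF is not among the documents, so this is open. If it is absent, the remedy costs more.

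These points limit the consequence but do not remove the gap. Adverse-event capture and the normal/abnormal reading depend on investigator judgement and give no counts by threshold. The 5.6.7 model covers dose escalation only, on Day -3 or Day 1 and Day 15, so it says nothing about later cycles, and a mean prediction does not replace individual outliers.

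**Conclusion.** The point holds for numeric QTcF. As written, the by-visit statistics, change from baseline and outlier counts in SAP 5.6.6 cover Part A1 in the lead-in and Cycle 1 only. At planned numbers, 60 of 100 Phase 1 patients (40 of 80 with one Part B cohort) and every ECG from Cycle 2 onward are outside them. This sits poorly with the All Treated population named in the same section and with the Part B ECG endpoint.

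The coverage result follows from the text and rests on no assumption beyond planned enrolment. The detection percentages are illustrative only. The analyses are descriptive, with no hypothesis at stake, and other outputs carry part of the QT information. The SAP should be changed, but this is not a failure of safety monitoring.

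**What to change.** In SAP 5.6.6:

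1. Add descriptive, change-from-baseline and outlier tables for local on-treatment QTcF: A2 and B at all visits, and A1 from C2D1. Use the triplicate mean where triplicates are taken, and include unscheduled ECGs when finding the maximum.
2. Show results by source. Take baseline from the same source as the follow-up value. For A1 the local baseline would be the screening ECG, because C1D1 falls after the lead-in dose.
3. Use as denominator the patients with a baseline and at least one post-baseline value from that source.
4. Label the existing table as Part A1, lead-in and Cycle 1, central ECG, with a matching denominator. If nothing else changes, this alone would stop it being read as covering all treated patients.
5. Check the eCRF. If it holds local QTcF only at screening, add the QT, RR and QTcF fields that protocol Table 12 already requires.

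The cost is SAP wording, a few more tables and possibly three eCRF fields. No ECGs are added. The downsides are noisier local readings, which display by source makes visible, and possibly some retrospective data entry for patients already treated.

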5.6.7. Time-Matched QTcF versus Plasma Concentration Analysis

Change from baseline QTcF (Δ QTcF) versus time-matched plasma concentration will be plotted for PK Lead-in Day -3 (for QD dosing) or Day 1 (for BID dosing if applicable) and Day 15 (for both QD dosing and BID dosing, if applicable) of Cycle 1 for PK/ECG Analysis Population in the Dose Escalation portion of the study. In addition, the relationship between plasma concentration of TAS3351 and Δ QTcF will be modeled using a linear mixed-effects model where Δ QTcF is the dependent variable, plasma concentration, nominal day (categorical), nominal time post-dose (categorical), and influence of baseline on intercept are independent

variables, and with random effect of patient on the intercept and slope under an unstructured covariance matrix. In case of convergence or estimation issues, model may be fit without random effect for concentration on the slope and/or intercept. Age, sex and body-weight may be included as a covariate. Additional covariates may be explored to be included in the model. Covariates will be added one at a time to the base model described above and compared using Akaike Information Criterion (AIC). If AIC of the model with covariate is less than that of the AIC of base model and p-value for covariate is less than 0.05 then the covariate will be retained in model. The relationship between plasma concentration of active metabolite TAS-05-14317 and Δ QTcF will be modeled using a similar mixed model as parent. Any interaction between TAS3351 and TAS-05-14317 may also be characterized. Note that for QTcF measurements collected in triplicate at nominal timepoints, the mean of the triplicate measurements will be used in the analysis.

The following will be presented in tabular form for TAS3351 and TAS-05-14317 separately:

- Slope of plasma concentration effect on Δ QTcF
- Standard error of plasma concentration effect on Δ QTcF
- P-value of slope of plasma concentration effect
- P-value of overall model fit (from the likelihood ratio test)

In addition, the predicted mean change from baseline QTcF (in milliseconds) will be presented for each dose level using the same linear mixed-effects models as described above, where plasma concentration is specified as the geometric mean C_{\max} for each dose level on a specific visit. The predicted mean change from baseline QTcF (in milliseconds) may also be presented for each dose level using the same linear mixed-effects models as described above, where plasma concentration is specified as the maximal observed concentration at each dose level. A double-sided 90% confidence interval for the predicted mean Δ QTcF will also be presented.

The following model assumptions will be evaluated by the indicated exploratory plots:

- Assumption 1: No drug effect on HR
 - Time course of mean Δ HR effects by dose will be plotted
- Assumption 2: QTcF interval is independent of HR
 - QTcF vs RR will be plotted
 - The adequacy of the correction formula will be assessed by determining the linear relationship of QTcF to RR. Adequacy will be evaluated based on the population QTcF:RR slope. If QTcF is determined to be an inadequate correction, then another fixed-formula rate correction may replace the primary endpoint of QTcF
- Assumption 3: No time delay between drug concentrations and Δ QTcF
 - Time course of mean concentrations and mean Δ QTcF by dose will be plotted
- Assumption 4: Linear C-QTcF relationship
 - Δ QTcF versus concentration will be plotted with a trend line included

If significant hysteresis is found, another model (e.g., Emax model, effect-compartment model) should be explored.

Goodness-of-fit plots, including but not limited to Model predicted vs observed $\Delta Q T c F$, Quartile-Quartile plot of residuals, Concentrations vs residuals, Baseline $Q T c F$ vs residuals, Time vs residuals, and Quantiles of concentrations and $\Delta Q T c F$ overlaid with slope of final model and when relevant for key stages during model development may be presented.

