8. PHARMACOKINETICS

8.1. Sample Collection

Blood samples for PK analysis and ECG sampling will be collected at specific time points listed in Table 13 (Table 14 in case BID dosing will be explored) and used to evaluate PK of TAS3351 and its active metabolite (TAS-05-14317). ECGs should also be obtained prior to on-site TAS3351 administration. When a 12-lead ECG is obtained at the same timepoint as a PK blood draw, the 12-lead ECG should be obtained first.

Detailed information about collection procedures including blood sampling, collection, processing, and sample shipment will be provided in a separate Laboratory Manual.

Table 13: Schedule for PK and ECG Sampling (QD Dosing)

Phase 1 Dose Escalation (Part A1)			
Day of Study ^a	Collection time relative to TAS3351 administration (time window ^b)	PK sample	ECG ^c
PK Lead-in, Day -3	Pre-dose (up to -30 minutes)		X
	0.5 hours (±10 minutes)	X	
	1 hour (±10 minutes)	X	X
	2 hours (±15 minutes)	X	X
	3 hours (±20 minutes)	X	
	4 hours (±25 minutes)	X	X
	6 hours (±35 minutes)	X	
	8 hours (±45 minutes ^d)	X	X
	24 hours (±2 hours)	X	X
	48 hours (±2 hours)	X	
	72 hours (± 2 hours ^e)	X	X
Cycle 1 Day 15	Pre-dose (up to -30 minutes)	X	X
	0.5 hours (±10 minutes)	X	
	1 hour (±10 minutes)	X	X
	2 hours (±15 minutes)	X	X
	3 hours (±20 minutes)	X	
	4 hours (±25 minutes)	X	X
	6 hours (±35 minutes)	X	
	8 hours (±45 minutes ^d)	X	X
	24 hours (±2 hours ^e)	X	X
Cycle 2 Day 1	Pre-dose (up to -30 minutes)	X	X (Local)
Cycle 3 Day 1	Pre-dose (up to -30 minutes)	X	X (Local)

Phase 1 “Backfill” (Part A2), Dose Expansion (Part B), and Phase 2 (Part C)			
Day of Study^a	Collection time relative to TAS3351 administration (time window^b)	PK sample	ECG^c
Cycle 1 Day 1	Pre-dose (up to -30 minutes)	X	X (Local)
	2 hours (±1 hour)	X	X (Local)
Cycle 2 Day 1	Pre-dose (up to -30 minutes)	X	X (Local)
	2 hours (±1 hour)	X	X (Local)
Cycle 3 Day 1	Pre-dose (up to -30 minutes)	X	X (Local)

^a For patients with TAS3351 dose interruptions, PK days might be postponed or waived upon discussion and written approval by the Sponsor. Additional optional PK samples may be collected if any safety concerns are identified. If no longer needed for PK evaluation, collection time points might be skipped upon written notification by the Sponsor.

^b Time window given for guidance; collection outside these windows will not be considered a protocol deviation as long as the exact time of dosing and sampling is documented.

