3.3. Determination of Sample Size

Part A:

Part A1: Phase 1 Dose Escalation

There will be up to 40 evaluable patients enrolled using the BOIN (Bayesian optimal interval design) design, [REDACTED] A minimum of 3 patients at each dose level are required.

Part A2: Backfill patients

Approximately 20 patients will be added for “back-fill” cohorts as needed in the Phase 1 Dose Escalation. The additional information from these “back-fill” patients will broaden the amount of safety and preliminary anti-tumor activity data for TAS3351 at a potential active dose levels to inform the selection of the RP2D of TAS3351.

Part B: Phase 1 Dose Expansion

Approximately 40 patients (20 patients per cohort) will be enrolled in the Dose Expansion part of this study. Sample size considerations were based on estimating the proportion of responders with certain precision. If there will be 9 responders, a sample size of 20 patients per cohort would allow to exclude the current standard of care ORR of 25% (90% CI: 27.4%, 68.0%) at 2-sided significance level of 10%.

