4.2. Populations for Analysis

The analysis populations in the study are defined in [Table 3](#).

Table 3: Definitions of Analysis Populations

Analysis Population	Definition
All Consenting Population	All patients who signed an informed consent form (ICF).
All Treated Population	All patients who received at least one dose of the study drug. This is the primary population for dosing, efficacy and safety analyses.
DLT Evaluable Population	All patients in the Dose Escalation, except backfill patients, who either experienced a DLT during the 1st cycle of treatment including PK lead-in period, or who completed the 1st cycle without experiencing a DLT and with at least 80% of planned study treatments administered. This is the specific population for DLT summarization.
PK Analysis Population	All patients who received at least one dose of study drug and have at least one post-dose TAS3351 and/or TAS-05-14317 plasma concentration measurement will be evaluated for PK; unless significant protocol

	deviations may have affected the data or if key dosing information is missing. This is the primary population for PK analysis.
PK/ECG Analysis Population	All patients who received at least one dose of study drug, have a baseline and at least one post-dose ECG value, and have time-matched plasma concentrations to at least one post-dose ECG value.
Pharmacodynamic/Biomarker Analysis Population	All patients in the All-Treated Population who have at least one evaluable baseline and one evaluable post-dose pharmacodynamic/biomarker datapoint for analyses.

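### The fallback for the concentration-QTcF model has no order and no minimum structure, so it permits a fit that treats each patient's repeated ΔQTcF values as independent

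*SAP*

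**What the plan says.** SAP section 5.6.7 fits ΔQTcF by a linear mixed model. The fixed part is listed as "plasma concentration, nominal day (categorical), nominal time post-dose (categorical), and influence of baseline on intercept are independent" variables. The random part is specified "with random effect of patient on the intercept and slope under an unstructured covariance matrix". The fallback is one sentence: "In case of convergence or estimation issues, model may be fit without random effect for concentration on the slope and/or intercept". No sequence of simplification is given, nor any minimum random structure, residual correlation structure or cluster-robust standard error.

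The tabulated outputs are the slope, its standard error, its p-value and an overall model-fit p-value. Predicted mean ΔQTcF follows at the geometric mean Cmax of each dose level: "A double-sided 90% confidence interval for the predicted mean Δ QTcF will also be presented". Section 5.6.7 takes these predictions from the same mixed models and applies a similar model to the metabolite TAS-05-14317.

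The analysis set is the PK/ECG Analysis Population, whose members must "have time-matched plasma concentrations to at least one post-dose ECG value" (SAP section 4.2). Its size is not stated. SAP section 3.3 caps dose escalation: "There will be up to 40 evaluable patients enrolled using the BOIN" design. Protocol section 8.1 fixes the matched sampling: "Blood samples for PK analysis and ECG sampling will be collected at specific time points listed in Table 13", with Table 14 for twice-daily dosing.

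**The concern.** With neither random effect, the model is ordinary least squares on repeated rows. A patient's rows are not independent. Under SAP section 7.1 each patient has one baseline, taken before the first dose, and every ΔQTcF value subtracts it. The measurement error in that baseline is therefore common to all of the patient's rows, and adjusting for baseline removes only part of it. Concentration also varies strongly between patients, because doses run from 50 to 700 mg/day. A between-patient covariate combined with within-patient correlation is the setting in which the ordinary standard error of a slope is too small.

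QT prolongation is a named risk (Protocol section 2.2.1.6), and the affected figures are the ones this analysis reports. The error can run either way: an apparent concentration effect that is not there, or an upper confidence limit for predicted ΔQTcF that sits below the true value.

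**Working it through.** The documents state no sample size, power, variance or significance level for this analysis, so there is no plan figure to reproduce.

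**1. Rows.** Once-daily, Table 13, post-dose times with both PK and ECG: Day -3 at 1, 2, 4, 8, 24, 72 h (6); Cycle 1 Day 15 at pre-dose, 1, 2, 4, 8, 24 h (6). Triplicates are averaged to one value.
- Maximum: 12 × 40 = 480.
- If the 8 h PK sample is waived after Dose Level 1, as a Table 13 footnote allows: about 10 × 40 = 400.
- Twice-daily, Table 14: 4 + 5 = 9 per patient, or 360 if all 40 were on that schedule.

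**2. Correlation from the shared baseline alone.** Let λ be the share of baseline variance that is true between-patient variance. Assume equal measurement error before and after dose and no other patient heterogeneity. Given the baseline, the shared error has variance λσ², and each row adds its own σ². Hence conditional ICC = λ/(1+λ).
- λ = 0.5: 0.5/1.5 = 0.33.
- λ = 0.16 to 0.41: ICC 0.14 to 0.29.
- Assumed between-patient SD 15 ms, error SD 6 ms: λ = 225/261 = 0.862, ICC = 0.862/1.862 = 0.46.

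Further heterogeneity between patients raises these values.

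**3. Slope test with both effects dropped.** Simulation under a true zero slope: 40 patients over six doses, 12 rows each, the SAP's fixed effects, two-sided 5% (an assumed level), 1,500-2,000 replicates per setting. Assumed: residual SD 5-7 ms, half-life 8-40 h, exposure CV 50%. The 0.33 row comes from a separate run of 600 trials per setting.

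| Conditional ICC (assumed) | Rejection |
|---|---|
| 0 | 5% |
| 0.04 | 9% |
| 0.14 | 18% |
| 0.29 | 30% |
| 0.33 | 32% |
| 0.37 | 34% |
| 0.45-0.50 | 34-41% |
| 0.57-0.68 | 39-46% |
| 0.74-0.78 | 43-49% |

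Fewer patients or rows change little: 39-41% with 24 patients, and 33% with the 8 h sample waived (15 and 6 ms SDs).

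**4. Cross-check by design effect.** DE = 1 + 11 × ICC × ρ, where ρ is the within-patient correlation of concentration; rejection = 2(1 − Φ(1.96/√DE)). The simulated 38% at ICC 0.46 gives 1.96/√DE = 0.878, DE = 4.98 and ρ = 3.98/(11 × 0.463) = 0.78. With that ρ:
- ICC 0.14: DE 2.20, rejection 19%.
- ICC 0.29: DE 3.50, rejection 30%.
- ICC 0.33: DE 3.84, rejection 32%.
- ICC 0.78: DE 7.71, rejection 48%.

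These agree with the table.

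**5. The 90% CI for predicted ΔQTcF** (top-dose geometric mean concentration, Day 15, 2 h). Coverage is 90% at ICC 0, 72-85% at 0.14-0.37 and 64-75% at 0.45 or above. With a true effect of 10 ms at the 700 mg Cmax and the 15 and 6 ms SDs, the upper limit falls below the truth in about 13% of trials, against a nominal 5%.

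**6. Alternatives.**
- Random intercept kept, slopes equal across patients: rejection 4.4-6.5%, CI coverage 88-92%.
- Random intercept only, slopes truly varying (SD 2, 5, 10 ms per simulated concentration unit): rejection 9%, 22%, 45%.
- No random effects, uncorrected patient-clustered SE: about 7-11%.
- No random effects, jackknife patient-clustered SE: 5-7%, including 6% at slope SD 5, where the unclustered fit gave 52%.

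**The case against.** The strongest reply is that the harmful branch is unlikely. A random slope with unstructured covariance is the part likely to fail, and the natural step is then to drop the slope and keep the intercept. In 550 simulated fits of the random-intercept model at conditional ICC of about 0.46 and above, none failed to converge and none gave a zero variance. The fit did fail at ICC near 0.04 (18 of 40 with one optimizer), but there the inflation is only to about 9%. Section 5.6.7 also calls the models behind its predictions mixed models, which sits badly with having no random effect at all. All of this stands as a limit on likelihood. It does not remove the permission, because the sentence lets the analyst drop both effects whatever the cause of the trouble.

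A second reply is that little hangs on the result. This is an exploratory Part A objective, the protocol states no formal hypothesis, no decision rule attaches to the slope p-value or the interval, and QTcF is also tabulated by category. That stands and limits severity.

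A reader might infer that the slope test will reject a true null some 36-46% of the time, on 480 rows from 40 patients. The documents do not support that. The rate needs a conditional ICC of about 0.45-0.75, and neither document gives an ICC, a QTcF SD, a half-life or a significance level for the slope. Forty is the cap on evaluable dose-escalation patients, not the PK/ECG count, and 480 assumes complete once-daily sampling with no waiver.

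**Conclusion.** The concern holds in a limited form. The fallback permits a fit that treats a patient's repeated ΔQTcF values as independent, and such a fit gives too small a slope standard error and too narrow a 90% CI whenever within-patient correlation is material. Some correlation is expected because the baseline is shared; under the stated assumptions the ICC is at least 0.33 once patients differ in true QTcF as much as measurement error does (λ of 0.5 or more).

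The size is conditional on that assumed ICC. It ranges from no harm at zero, through moderate inflation at 0.14-0.29, to rejection of a true null in roughly three to five trials in ten at 0.33 or above. It applies only if the model has trouble and both effects are dropped. Given that, and the exploratory status, severity is minor to moderate.

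Keeping the random intercept is not by itself a full cure, since the test remains anti-conservative if slopes differ between patients.

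**What to change.** Replace the fallback sentence in SAP section 5.6.7 with a fixed sequence that never treats a patient's rows as independent:

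1. Random intercept and slope with diagonal covariance.
2. Random intercept only, with small-sample-corrected patient-clustered standard errors.
3. If that also fails, the same fixed effects with small-sample-corrected (for example jackknife) patient-clustered standard errors.

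Apply the sequence to the TAS-05-14317 model and to the 90% CI for predicted ΔQTcF, and report which step was used. The jackknife correction was checked on the fit with no random effects (step 3); its use at step 2 rests on the same reasoning but was not simulated.

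The change is a short text edit and needs no new data. Its cost is wider confidence intervals than the unclustered fit would give.
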